Official title of study: UCI 14-92 / HS #2015- 1889: Phase IV Study of Daylight Photodynamic Therapy

with Aminolevulinic Acid for Actinic Keratoses

NCT Number: NCT03327831

Date of Document: July 1,2015

Protocol/Methods:

The study was designed prospectively to have 90% power to detect a 50% change in number of AKs. The study was approved by the University of California Institutional Review Board. A total of 30 patients were recruited from July 2015-October 2016 at the University of California, Irvine Department of Dermatology. Two patients were lost to follow up. Study inclusion criteria were age >18 years old with >10 actinic keratoses measuring >3mm each on the face or scalp. Exclusion criteria were history of photosensitive skin disorder, current pregnancy, or use of topical or oral retinoids, imiquimod, ingenol mebutate, fluorouracil, or photosensitizing medications in the past 3 months prior to PDT or during the 6 month study period. Patients were also excluded if the weather was rainy on the intended day of treatment.

Patients were instructed to wash their faces using a washcloth with warm, soapy water for 5 minutes in order to remove excess oil and improve drug penetration and then gently curetted with a 4mm non-disposable curette.

After curettage, the ALA (Kerastick®, DUSA) was applied first as spot treatment to the individual lesions and then as field treatment to the entire treatment area. Following ALA application, an avobenzone-containing chemical sunscreen was applied. The chemical sunscreen was utilized to block ultraviolet light (and possible sunburn from daylight exposure) while allowing wavelengths above 400nm to pass through and activate the PpIX.

After application patients were sent outdoors or home with a handheld luxometer (Suncheck Instruments, Model HS1010) and detailed written instructions. All patients were instructed to begin their daylight exposure within 30 minutes of ALA application and to remain in the daylight for 2 hours. We specifically asked patients to be in a shaded area “where you can see the sky but not the sun.” During daylight exposure, patients recorded pain (scale of 0-10), lux, the weather (raining, cloudy, partly cloudy, sunny) at times 0, 1 hour, and 2 hours, and patient

satisfaction (not satisfied, slightly satisfied, moderately satisfied, or very satisfied). After daylight exposure all patients were instructed to apply physical sunscreen with titanium or zinc oxide and a wide brimmed hat in order to block visible light and prevent further PPIX activation. The patients were not instructed to wash off the ALA afterward. They were instructed to go indoors for the following 48 hours. All patients were given prophylactic valacyclovir 500 mg BID for 7 days to prevent herpes simplex reactivation and possible eczema herpeticum.

Patients were evaluated and photographed at time 0 days, 3 days, 3 months, and 6 months after treatment and AK counts were performed at 0 days, 3 months, and 6 months. Summary statistics were calculated and a Pearson correlation coefficient test was performed (Stata/IC, Version 15) to assess the relationship between lux received and AK count at 6 months.

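### The stated 90% power refers to a 50% change in AK count, but no estimate with uncertainty and no test is named for that change

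*Combined protocol and SAP*

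**What the plan says.** All the relevant text is in the Protocol/Methods section of the combined protocol and SAP.

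- **Design target (first paragraph):** "The study was designed prospectively to have 90% power to detect a 50% change in number of AKs". No test, alpha, SD, measurement scale or time point accompanies it.
- **Numbers (same paragraph):** "A total of 30 patients were recruited from July 2015-October 2016" and "Two patients were lost to follow up". Neither sentence is linked to the power statement.
- **Entry (same paragraph):** patients had to be adults "with >10 actinic keratoses measuring >3mm each on the face or scalp".
- **Data (last paragraph):** "AK counts were performed at 0 days, 3 months, and 6 months".
- **Analysis (last paragraph):** "Summary statistics were calculated and a Pearson correlation coefficient test was performed", the latter "to assess the relationship between lux received and AK count at 6 months". The variables summarised and the kind of summary are not named.

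No comparison group is described.

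**The concern.** Power belongs to a particular test of a particular quantity. Here the quantity is a change in the number of AKs, yet no analysis of change is named, although counts at day 0, 3 months and 6 months were available. The one named test asks something else: whether patients who received more light had fewer or more lesions at 6 months.

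Followed exactly as written, the plan gives no stated precision for its only design target. A reader could not tell how well a 50% change was estimated, or whether it was distinguishable from a smaller one. The 90% figure cannot be checked against any analysis. The target itself is open: it could be the mean of within-patient percent changes, the change in the mean count or a ratio of rates, at 3 or at 6 months.

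**Working it through.** **1. Can the 90% be reproduced?** No. The needed inputs are set out below.

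| Input | In the document? |
|---|---|
| Power | 90% |
| Effect | 50% change in AK count; scale and time point not given |
| Patients | 30 recruited, 2 lost; not tied to the 90% |
| Test, alpha, sidedness | not given |
| SD of change | not given |
| Baseline mean | not given; entry minimum only (more than 10 lesions) |

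**2. Can the named test stand in for an analysis of change?** Write Y0 and Y6 for a patient's counts at day 0 and 6 months, and L for lux. The test uses r = cov(L, Y6) / [SD(L) × SD(Y6)].

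- Y0 does not appear in it.
- Replace every Y6 by c × Y6 with c > 0. The numerator and denominator are both multiplied by c, so r and its p-value stay the same. Halving every 6-month count (c = 0.5) leaves the result untouched.

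A simulation agrees. With 28 patients, an average 50% reduction and lux unrelated to count (all distributions assumed), the Pearson test rejected in 4.7% of runs, about its nominal 5%. A paired t-test on the counts rejected in every run.

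**3. What would the power be under one reading?** The following are assumptions, not document figures: a paired t-test, two-sided alpha 0.05, a mean within-patient reduction of 50 points, and a range of SDs. The standardised effect is d = 50 / SD. Exact power comes from the noncentral t with n − 1 degrees of freedom and noncentrality d × √n.

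| Assumed SD (points) | d | Smallest n for 90% | Power at n = 28 | Power at n = 30 |
|---|---|---|---|---|
| 40 | 1.25 | 9 | >99.9% | >99.9% |
| 50 | 1.00 | 13 | 99.9% | >99.9% |
| 60 | 0.83 | 18 | 98.9% | 99.3% |
| 80 | 0.625 | 29 | 89.0% | 91.1% |
| 100 | 0.50 | 44 | 72.3% | 75.4% |

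Power equals 90% at an SD of 81.6 points for n = 30 and 78.7 points for n = 28.

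**4. Which of those SDs are possible?** A reduction cannot exceed 100 points. If no patient worsens, every value lies between 0 and 100. A variable on that range with mean 50 has variance at most (50 − 0) × (100 − 50) = 2,500, so its SD is at most 50. The rows at 60, 80 and 100 therefore require some patients to finish with more lesions than they started with, and the last two require substantial worsening. Without worsening, 13 patients suffice on this reading.

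**5. What precision might a reader want to see?** The half-width of the 95% t interval is t(0.975, n − 1) × SD / √n. At the no-worsening limit with n = 28 this is 2.052 × 50 / 5.292 = 19.4 points. This is only an illustration at the largest SD allowed, not an estimate for this trial. The 28 is also assumed (30 − 2), since the visit at which the two patients were lost is not given.

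**The case against.** **The Pearson test was never offered as the analysis of change.** It has its own stated purpose, and nothing calls it primary or confirmatory. This stands: the fault is an omitted analysis, not a wrong one, and the lux correlation needs no relabelling.

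**Summary statistics may already include the change in count and its spread.** They may, and a reader should not infer that change went unexamined. But no variable, summary or interval is named, so the plan does not commit to a measure of uncertainty for its design target.

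**Thirty patients may be ample.** This also stands. A reader of the power table might infer that 30 is too few or that the 90% is wrong. The documents support neither. The power falls to about 90% or below at n = 28 to 30 only for SDs near 80 points or more, which on the percent-change scale need substantial worsening in some patients. Nor can one say that the study was sized at 30 to reach 90%, because the document never links the two.

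**The account is in the past tense and there is no control group, so a test of change against zero adds little.** This is fair. An estimate with a confidence interval is enough, and a paired test is optional.

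**Conclusion.** The concern holds in a narrow form and should be fixed. The sole design target, "90% power to detect a 50% change in number of AKs", has no named estimate with uncertainty and no named test, and the one named test cannot address change. These two statements rest on the text and on the algebra of the correlation coefficient, with no numerical assumption.

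The 90% is unverifiable rather than wrong. Under one assumed reading (paired t, two-sided 0.05, mean reduction of 50 points), the number needed ranges from 9 at an SD of 40 to 44 at an SD of 100. It is at most 13 if nobody worsens. The documents cannot place the trial within that range, so no shortfall in sample size is shown.

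**What to change.** 1. **Report the change.** For each patient compute 100 × (Y0 − Y6) / Y0. This is always defined, because entry requires more than 10 lesions. Give the mean, the number of patients analysed and a 95% t interval. A paired test is optional. Report the 3-month change in the same way as secondary.
2. **Respect any earlier definition.** If an earlier record defines the 50% change on another scale or at another time point, use that as the main analysis. If there is none, label the analysis as specified after data collection.
3. **Word it as change from baseline.** With no control group described, the result cannot separate a treatment effect from spontaneous change or from the effect of selecting patients with many lesions.
4. **Support or drop the 90%.** State the original test, alpha, SD, scale and time point. If they cannot be recovered, remove the figure and rely on the observed interval. If a power illustration is kept, mark alpha, SD and the number at 6 months as assumed, and state the 50-point limit on the SD when no patient worsens.

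The cost is some wording and a small analysis of counts already collected, with no extra patients or visits. The downside is that the 90% figure may be lost and the added analysis may carry a post hoc label.

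### Drug use after PDT is written as an exclusion criterion; applied literally it would remove treated non-responders and bias the AK reduction upward (minor: no removal is reported)

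*Combined protocol and SAP*

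**What the plan says.** All the relevant text is in the Protocol/Methods section of the combined protocol and SAP.

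- **Eligibility.** The criterion begins "Exclusion criteria were history of photosensitive skin disorder, current pregnancy, or use of topical or oral retinoids, imiquimod, ingenol mebutate, fluorouracil" and ends "photosensitizing medications in the past 3 months prior to PDT or during the 6 month study period". One sentence therefore covers a period before treatment and a period after it, both under the label of exclusion.
- **Patient flow.** "A total of 30 patients were recruited" and "Two patients were lost to follow up". No other loss, withdrawal or removal is mentioned, and the number analysed is not stated.
- **Outcome times.** "AK counts were performed at 0 days, 3 months, and 6 months".
- **Analysis.** "Summary statistics were calculated and a Pearson correlation coefficient test was performed", the latter "to assess the relationship between lux received and AK count at 6 months".

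The section names no primary endpoint or analysis set. It gives no rule for a treated patient who later uses a listed drug. It describes one procedure for everyone and no control group; that the study is single-arm is inferred from this.

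**The concern.** An eligibility rule should rest on facts known before treatment. Here, half of the window lies after PDT and covers the 3-month and 6-month counts. Intended use can be asked about at enrolment, but actual use cannot be known then.

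The drugs in question make this more than a matter of wording. Fluorouracil, imiquimod and ingenol mebutate are treatments for AKs, and a patient whose lesions persist after PDT is a likely person to start one. If starting it makes the patient excluded, membership of the analysed group depends on the outcome. With no comparator to share the distortion, the AK reduction would look larger than it was, and a larger sample would not correct it. Removal for a retinoid or a photosensitizing drug, if unrelated to response, has no clear direction.

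The before-after AK change is exposed to this. The lux correlation also depends on who is analysed, because it uses the 6-month count.

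**Working it through.** **The plan's own figure.** The section claims "90% power to detect a 50% change in number of AKs". It cannot be reproduced or refuted, because significance level, sidedness, standard deviation and test are not given. Assuming a paired comparison of percent change at two-sided 0.05 with 30 patients, the normal approximation gives 90% power when SD = 50 × √30 / (1.960 + 1.282) ≈ 84.5 points (about 82 with the t distribution). The present point does not depend on this figure; the 50% serves below only as an anchor.

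**Which readings create bias**

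| Reading of the post-PDT clause | Effect on who is analysed |
|---|---|
| Restriction on medication, patients kept | No selection bias by itself |
| Removal rule, nobody met it | None |
| Removal rule, patients removed for reasons unrelated to response | No clear direction |
| Removal rule, patients removed because AKs persisted | AK reduction biased upward |

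The text does not say which reading applies.

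**Size if the last reading applied**

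Inputs:
- Patients with follow-up: 30 − 2 = 28. This assumes that all 30 recruited were treated and that there were no other losses.
- R, the mean percent reduction in patients kept: assumed 50% (anchor) or 70%.
- x, the percent reduction after PDT alone in a removed patient: assumed 0%, equal to R, or 100%.
- k, the number removed: not in the documents; 0, 1 and 2 are shown.

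The reported mean would be R. The mean over all 28 would be [(28 − k)R + kx] / 28. The bias is the difference, k(R − x) / 28.

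| k | x | R = 50% | R = 70% |
|---|---|---|---|
| 0 | – | 0 | 0 |
| 1 | 0% | 50/28 = +1.8 | 70/28 = +2.5 |
| 1 | R | 0 | 0 |
| 1 | 100% | −50/28 = −1.8 | −30/28 = −1.1 |
| 2 | 0% | 100/28 = +3.6 | 140/28 = +5.0 |

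For example, with k = 1, x = 0 and R = 50, the mean over all 28 is 27 × 50 / 28 = 48.2%, against a reported 50%. Fixing the all-patient mean instead changes little: 28 × 50 / 27 = 51.85 (+1.85) and 28 × 70 / 27 = 72.59 (+2.59).

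**The case against.** The strongest reply is that the sentence is ordinary shorthand for a washout before treatment plus a ban on the same drugs during follow-up. On that reading nobody is removed and there is no selection bias. The patient flow fits it: two losses to follow-up are the only attrition reported. An upward bias would need three things that the documents do not state: that a patient started a listed drug, that the patient was removed for it, and that the reason was failure of PDT. Even then the shift is modest per patient.

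Most of this stands, and it sets the weight of the point. It does not remove the point. The clause is labelled an exclusion, the number analysed is not given, and no analysis set shows which reading was followed.

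Two stronger readings are tempting:

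- A reader might infer that treated patients were in fact dropped and that the AK result is biased. Nothing in the documents shows this.
- A reader might infer that removing non-responders takes out the highest 6-month counts and so weakens the lux correlation by a calculable amount. That does not follow. A patient who started an AK drug would probably have a 6-month count lowered by that drug, so the counts removed need not be the high ones. No size is claimed for the correlation.

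**Conclusion.** The point holds in conditional form and is minor. As written, the criterion makes inclusion depend on an event after PDT that can itself depend on persistence of AKs, in a study with no described comparator. If it was applied literally to patients whose PDT had failed, the AK reduction is overstated by about 1.8 to 2.5 points per patient with no reduction removed from 28. If nobody was removed, or the clause only restricted medication, the selection bias is zero.

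The range rests on the assumed 50% and 70% reductions, on a mean of per-patient percent changes as the summary, and on all 30 recruited patients having been treated. The actual size and direction cannot be derived from the documents.

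**What to change.** 1. Apply the eligibility exclusion only to information available before PDT. Leave any restriction on medication during follow-up unchanged, and state it separately from eligibility.
2. Analyse all treated patients with available AK counts as the main set, and give the number at each time.
3. Report how many treated patients used a listed drug after PDT, including zero.
4. Show the AK change and the lux correlation with and without those patients as a sensitivity analysis. Label it post hoc: the section already reports the counts and statistics in the past tense.

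**Cost.** The text change is about two sentences. A record of drug use after PDT is needed, and the section does not describe collecting one. Post-drug counts kept in the main set may partly reflect the other drug, which is why the sensitivity analysis is needed. That comparison does not guarantee bounds: for a patient who started a drug because PDT failed, keeping the post-drug count and leaving the patient out can both flatter PDT. The number affected must therefore be read alongside it. The reported reduction may become slightly less favourable. If no treated patient used a listed drug, saying so closes the point and no result changes.

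### Lux readings at 1 and 2 hours may depend on the patient's own pain, so correlating an undefined 'lux received' with the raw 6-month AK count can be confounded in either direction

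*Combined protocol and SAP*

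**What the plan says.** Everything on this point is in the Protocol/Methods section of the combined protocol and SAP.

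- **Setting.** "After application patients were sent outdoors or home with a handheld luxometer". No staff observation, fixed position or log of movement is described.
- **Position.** "We specifically asked patients to be in a shaded area", with the sky in view but not the sun. No light level is set.
- **Duration.** Patients were told "to begin their daylight exposure within 30 minutes of ALA application and to remain in the daylight for 2 hours".
- **Recording.** "patients recorded pain (scale of 0-10), lux, the weather (raining, cloudy, partly cloudy, sunny) at times 0, 1 hour, and 2 hours".
- **Analysis.** The final paragraph names summary statistics and one test, a Pearson correlation "to assess the relationship between lux received and AK count at 6 months". It does not say how three readings become one lux value, and it mentions neither pain nor baseline count in this test.
- **Baseline.** "AK counts were performed at 0 days, 3 months, and 6 months", so a day-0 count exists. Entry requires more than 10 lesions, with no stated upper limit.

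**The concern.** The correlation treats lux as something set from outside the patient. The time-0 reading comes close to that. The 1-hour and 2-hour readings may not, because by then a patient in pain could have moved to darker shade and still been following the instruction. Lux would then partly record the patient's reaction. If whatever caused the pain also affects the 6-month count, lux and count are linked by a route other than the effect of light.

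This differs from meter error or season, and more readings of the same kind would not remove it. At stake is the plan's only named test: a real light effect could be understated or overstated, or an absent one could appear as a weak association.

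**Working it through.** **1. The plan's own power figure.** "The study was designed prospectively to have 90% power to detect a 50% change in number of AKs", and "A total of 30 patients were recruited". This concerns the change in count, not lux. It cannot be reproduced, because the significance level, sidedness and SD are not given. Assuming a two-sided 5% level and a paired z formula, d = (1.960 + 1.282)/√30 = 0.592. The SD of change would have to be 0.5/0.592 = 0.85 of the baseline mean (0.82 with the t distribution). Nothing here bears on the lux test.

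**2. What the lux test can detect.** Take n = 30 - 2 = 28, assuming both patients lost to follow-up lack a 6-month count. By Fisher's z at a two-sided 5% level, the smallest detectable |r| is:

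- 80% power: tanh((1.960 + 0.842)/√25) = 0.51
- 90% power: tanh((1.960 + 1.282)/√25) = 0.57

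**3. Direction of bias.** All coefficients below are assumptions, chosen only to show sign. L0 (time-0 lux), S (susceptibility to the reaction), B (baseline burden) and the noise terms e, e1, e2 and e3 are independent with variance 1.

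- Pain: P = 0.4·L0 + a·S + c·B + 0.8·e
- Lux at 1 and 2 hours: 0.9·L0 - 0.5·P + 0.3·e1 (or e2)
- Mean of the three readings: D = 0.8·L0 - (a/3)·S - (c/3)·B - 0.267·e + 0.1·(e1 + e2)
- 6-month count (standardised): Y = -0.35·D + s·S + b·B + 0.7·e3

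The unadjusted slope of Y on D is -0.35 - (s·a/3 + b·c/3)/Var(D), where Var(D) = 0.64 + (a/3)² + (c/3)² + 0.071 + 0.02.

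| What drives pain | a, s | c, b | Bias | Slope (truth -0.35) |
|---|---|---|---|---|
| Nothing else linked to outcome | 0, 0 | 0, 0 | 0 | -0.35 |
| Reaction that improves clearance | 0.6, -0.4 | 0, 0 | 0.08/0.771 = +0.10 | -0.25 |
| Baseline burden | 0, 0 | 0.6, 0.6 | -0.12/0.771 = -0.16 | -0.51 |
| Both | 0.6, -0.4 | 0.6, 0.6 | -0.04/0.811 = -0.05 | -0.40 |
| Both, reaction stronger | 0.6, -0.6 | 0.3, 0.6 | 0.06/0.781 = +0.08 | -0.27 |

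A simulation of 400,000 patients agrees with these slopes to within 0.003. With no true light effect, the second and third rows give +0.10 and -0.16.

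Time-0 lux is unrelated to S and B in this model. Its slope is -0.35 × 0.8 = -0.28 in every row, and 0 when light has no effect. It falls short of -0.35 because one reading is only a proxy for the whole exposure.

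Adjusting for baseline count restores -0.35 in the burden row. It leaves -0.25 in the reaction row and gives -0.25 in the fourth row, where the two biases had partly cancelled. Adjusting for pain changes little (-0.25 and -0.50 in the second and third rows).

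**4. Size in trials of 28.** Assumed inputs: log-normal lux (log SD 0.6 between and 0.3 within patients); light effect 0.5 logit per SD of log lux; susceptibility 0.8 logit per SD; 15 AKs each, except varying counts (log SD 0.5) in the burden case. The 30% with most pain halve their later lux. Significance needs |r| > 0.374.

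| What drives pain | Mean r, three-reading average: no one moves | 30% halve later lux | No true effect: average | No true effect: time-0 |
|---|---|---|---|---|
| Reaction that improves clearance | -0.42 | -0.32 | +0.14 | 0.00 |
| Baseline burden | -0.32 | -0.38 | -0.09 | 0.00 |
| Unrelated to outcome | -0.42 | -0.41 | | |

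In the last row, with movement, power is about 62% for the average and 50% for time-0.

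**The case against.** A reader might infer that pain-driven movement biases the test toward no effect, masking or even reversing a light benefit. The documents do not support that.

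- A lower reading in deeper shade is light truly not received, so movement alone is not measurement error. Bias needs a cause of pain that also affects the outcome, and the documents name none.
- Fixing the direction means assuming that strong reactors clear better and that baseline burden plays no part. Entry has no stated upper limit on lesions and the outcome is the raw count, so the opposite path is equally open.
- With a true light effect, a significant reversed correlation occurred in about 0.1% of simulated trials or fewer.

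It is also fair to say that patients had written instructions to stay out for two hours with the sky in view, which limits movement. No text reports that anyone moved, how much pain occurred, or that pain predicted response. And because the lux variable is undefined, the later readings may not be used at all.

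A second tempting step is to rest the conclusion on time-0 lux whenever lux falls more in patients with more pain. That trigger cannot separate harmless from biasing movement. When pain moved patients but was unrelated to clearance, the fall in lux still tracked pain in over 99% of simulated trials, yet the average was the better measure.

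These objections remove any fixed direction and any switching rule. They leave the open pathway, the missing definition and the absence of any stated adjustment.

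**Conclusion.** The concern holds in conditional form. If the 1-hour and 2-hour readings enter the lux variable, its unadjusted correlation with the raw 6-month count can be confounded through pain. The sign depends on what drives pain, and the documents do not settle that. Under the assumed inputs the shift in mean r is about 0.10 toward zero, 0.06 away from it, or 0.01. With no true light effect, the spurious mean r is about +0.14 or -0.09. These sizes rest on an assumed 30% of patients halving their later lux and are not estimates for this trial. The test is imprecise in any case: 28 patients give 80% power only for |r| of 0.51 or more.

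**What to change.** 1. State which readings form the lux variable and how they are combined.
2. Report the time-0 lux correlation beside the main one, labelled as a sensitivity analysis. The text describes the study in the past tense, so call it post hoc if the data have already been analysed.
3. Tabulate the change in lux from 0 to 1 to 2 hours against the preceding pain score, to show whether lux fell more after higher pain.
4. Include baseline AK count in the lux analysis. This addresses the burden path only; it does not remove bias from a reaction that improves clearance, and it can expose that bias where the two had been cancelling.
5. Do not move the conclusion to time-0. If the two results differ, describe the lux-response result as inconclusive.

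The cost is one more analysis, one table and one covariate, all from data already collected. The drawback is that a single reading is a noisier proxy for total light. If no one moves, the illustrative simulations give about 50-57% power for time-0 against 58-65% for the average, so a weaker time-0 result does not by itself show confounding.

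### The only named test relates lux to the raw 6-month AK count, so starting lesion burden is mixed with response and the 3-month count adds nothing to precision

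*Combined protocol and SAP*

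**What the plan says.** The final paragraph of Protocol/Methods gives the visits and the statistics together. On outcomes: "AK counts were performed at 0 days, 3 months, and 6 months". On analysis: "Summary statistics were calculated", without detail, followed by a Pearson correlation "to assess the relationship between lux received and AK count at 6 months". No change score, baseline adjustment, repeated-measures model or test at 3 months is named, and no time point is called primary.

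The opening paragraph gives the numbers: "A total of 30 patients were recruited from July 2015-October 2016" and "Two patients were lost to follow up". When those two left is not stated. The design claim there is "90% power to detect a 50% change in number of AKs", which concerns change in AK number, not the lux relationship. Eligibility sets a floor on the lesion count and no ceiling. Lux was recorded "at times 0, 1 hour, and 2 hours" of exposure; how the three readings become one value per patient is not stated.

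**The concern.** Patients start with different numbers of lesions. A raw 6-month count therefore reflects where a patient began as well as how far the lesions cleared, and the lux question is about clearance. Leaving the day-0 count out puts between-patient variation in burden into the outcome, where it dilutes any lux effect. The 3-month count is a second post-treatment measurement of the same response, and the test makes no use of it.

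At about 28 patients this matters for reading the result. A non-significant correlation could easily be taken as evidence that light exposure is unimportant, when the test had only a moderate chance of detecting a moderate relationship.

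**Working it through.** **The plan's own figure.** The stated 90% power cannot be reproduced, because no SD, alpha or test is given. With a paired t-test at two-sided 0.05 and n = 30, 90% power needs a standardised effect of 0.612. A 50-point change then implies an SD of percentage change of about 82 points. At n = 28 the effect needed is 0.636 and the SD about 79. This says nothing about the lux test, for which no power is stated.

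**Inputs.**
- From the documents: 30 recruited and 2 lost, so about 28 with a 6-month count; counts at day 0, 3 months and 6 months.
- Assumed: two-sided alpha 0.05; lux-count correlation r of 0.3 or 0.4; correlation rho between counts of 0.3 to 0.9; equal variances; lux unrelated to starting burden.
- For brevity one rho serves for both the day-0/6-month and the 3-/6-month correlation. In practice they may differ.

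**Planned test.** By Fisher's z, power = Φ(atanh(r)·√(n−3) − 1.96), plus a negligible opposite tail. For r = 0.4: atanh(0.4) = 0.424; 0.424 × √25 = 2.118; Φ(0.158) = 56%. For r = 0.3 it is 34%. The smallest r detectable with 80% power is tanh((1.96 + 0.842)/5) = 0.51.

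**Adding the 3-month count.** Averaging two counts multiplies the outcome variance by (1 + rho)/2, so r becomes r·√(2/(1 + rho)) if lux has the same effect at both visits. At rho = 0.5: 0.4 × 1.155 = 0.462; atanh = 0.500; Φ(2.498 − 1.96) = 70.5%.

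**Adjusting the 6-month count for day 0.** Residual variance is multiplied by 1 − rho², so r becomes r/√(1 − rho²), with one degree of freedom used (n − 4 = 24). At rho = 0.5: 0.462 again; Φ(0.500 × √24 − 1.96) = 69%.

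**Both together.** The variance factor is (1 + rho)/2 − rho².

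Power at r = 0.4:

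| rho | Planned | 3- and 6-month mean | 6-month, baseline-adjusted | Mean, baseline-adjusted |
|---|---|---|---|---|
| 0.3 | 56% | 78% | 59% | 83% |
| 0.5 | 56% | 71% | 69% | 88% |
| 0.7 | 56% | 64% | 87% | 98% |
| 0.9 | 56% | 59% | >99% | not shown |

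The last cell is omitted because r = 0.4 and rho = 0.9 cannot both hold there: the implied correlation exceeds 1. At r = 0.3 the planned 34% becomes 50%, 44%, 39% and 36% with the mean of two counts.

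The two remedies work in opposite directions. The 3-month count helps most when counts are weakly correlated, and the baseline helps most when they are strongly correlated.

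**If lux matters more at month 6.** Let r be 0.4 at month 6 and 0.4 × 0.20/0.35 = 0.229 at month 3. The correlation with the mean is (0.4 + 0.229)/√(2(1 + rho)), which is 0.390, 0.363 and 0.341 at rho 0.3, 0.5 and 0.7. Power of the unadjusted mean is then 54%, 48% and 43%, against 56% for month 6 alone.

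**The two lost patients.** Even with both restored to the 6-month test (n = 30), power at r = 0.4 is only 60%.

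**The case against.** The strongest reply is that a single 6-month endpoint is a deliberate and respectable choice. It matches the length of the study, and pooling with month 3 asks a different question. The 3-month counts may already appear in the summary statistics. All of this stands, and it is why the 6-month estimate should remain the main one.

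The gain from the 3-month count also rests on a correlation the documents do not give. At rho = 0.9 it is about 2 points. Pooling can lose power if the lux effect grows. Both points stand, and the size must be shown as a range. They do not touch the baseline adjustment, which keeps the 6-month question and gains most where rho is high.

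The text is in the past tense, so a changed analysis would now be a reanalysis. That also stands, and it affects labelling rather than merit.

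A reader might infer more than the documents support:
- That a 3-month count exists for every patient. It is scheduled; completeness is not reported.
- That the 6-month count is known to be unreliable. No SD or reliability figure is given.
- That half the outcome information is thrown away. Two correlated counts do not carry twice the information: averaging cuts variance by 25% at rho = 0.5 and by 5% at 0.9.
- That the lost patients could be recovered through their 3-month counts. This is only possible, since the timing of their loss is not stated.
- That the planned correlation is biased. That would need lux to be related to starting burden, and nothing in the documents shows this.

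**Conclusion.** The point holds as a loss of precision and a poorly targeted outcome. The named test uses one of three scheduled counts and does not separate response from starting burden. It is neither an internal contradiction nor an invalid test.

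At n = 28, r = 0.4 and two-sided alpha 0.05, baseline adjustment alone moves power from 56% to about 59%, 69% or 87% (rho 0.3, 0.5, 0.7). Averaging in the 3-month count, without baseline adjustment, adds about 21, 14, 8 or 2 points (rho 0.3, 0.5, 0.7, 0.9) under an equal lux effect at both visits. The unused day-0 count is thus the larger omission once rho is clearly above 0.5.

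These are closed-form approximations for continuous outcomes. They indicate the scale of the gain but are not power figures for the count model proposed below.

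**What to change.** Replace or supplement the raw Pearson test with a log-link count model of the 3- and 6-month counts. Use a patient random effect, or GEE with small-sample standard errors, with log day-0 count, visit, log lux and visit-by-lux as terms. Define the single lux value per patient. Report the 6-month lux rate ratio with 95% CI as the main estimate and the pooled 3/6-month rate ratio as supportive.

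With visit-by-lux in the model and near-complete data, the 6-month estimate gains mainly from the day-0 count, while the 3-month count sharpens mainly the pooled estimate. If 6 months alone is preferred, keep the day-0 adjustment and state that the 3-month counts are descriptive. If the model is run after the original test has been seen, label it as a reanalysis.

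The cost is a little more analysis work and no new data. The pooled estimate loses power if lux matters more at month 6 than at month 3 (in the example above, about 2 points at rho 0.3, 9 at 0.5 and 14 at 0.7), so it should not replace the 6-month estimate.
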